Because this is a feasibility study, primary outcomes of interest are recruitment (consent) rate, time required to complete initial tele-medicine assessment in the ED, time needed to administer XR-NTX in the ED, total ED length of stay, time to first follow up after the initial ED encounter, number of cell phones issued by the study, retention and follow up rates over the 3-month study

period, retention rate with other providers in San Francisco, number of doses of XR-NTX received during the study period and intervals between doses, and barriers to and facilitators of follow-up after the initial ED visit.

We will also collect pilot data on the following for statistical analysis:

Predictor Variable: Multi-modal treatment with Extended Release Naltrexone and case management

Primary Outcome: Change in the number of Emergency Department visits for alcohol-related complaints. [(# of ED visits for alcohol related complaint in 12 months after enrollment) - (# of ED visits for alcohol related complaint in 12 months before enrollment)].

Secondary Outcomes: number of standard alcoholic drinks consumed per week, number of days of heavy drinking, overall substance use severity (change in AUDIT score), change in alcohol-related social/occupational/psychological problems identified on SIP-2R, change in PEth, and change in urine ethyl glucuronide

Cost analysis: This study will not provide precise estimates of efficacy or costs. However, we will use our results to perform a basic cost analysis to guide future research. We will estimate: overall cost and cost per patient (medications, case management, follow-up visits), cost per avoided ED visit, cost per avoided hospitalization, program cost vs expected medical cost saved. All costs will be estimated at the societal perspective

Potential confounding variables or covariates, justifications:

There are several potential confounders which we will measure such as number of doses of XR-NTX received, willingness to change, engagement in other, baseline substance use severity, housing status, psychiatric and medical comorbidity, and basic demographic variables such as age and sex. The primary strategy employed to combat these cofounders is the selection of the primary outcome. Since the outcome is a change from the patient's baseline ED usage from the prior year each patient serves as their own control. Thus they are matched for many of the possible confounders.

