The risk of bias is substantial given that all enrollees are to be treated with XR-NRT and the study is not randomized or blinded and the population of interest is at high risk of being lost to follow up. We intend to conduct both an intention to treat analysis and a per protocol analysis, though our sample size may limit the utility of this approach. We will employ an independent data analyst to collect the ED visit counts and perform the final statistical analysis.

Statistical issues:

Statistical Test: Paired T Test

Hypothesis:

ED initiated Treatment of alcohol use disorders with multi-modal therapy reduces alcohol related ED visits in patients with frequent ED visits for alcohol related complaints

Sample Size:

We will enroll 25 patients. As a feasibility study our sample size was chosen as it represents a reasonable patient load for a single case manager. Because this population is difficult to retain in treatment, we anticipate the drop-out rate will be significant. Patients who drop out of the study (either withdraw or are lost to follow up) will be replaced with new enrollees until 25 patients have been recruited into the study. The goal of this practice is to maximize the benefit to the patient population, avoid wasting donated study medication, and to allow the research team to optimize recruitment and retention strategies.

Last year 42 patients presented to the UCSF Emergency Department at least 4 times for an alcohol related complaint. Of this group the mean number of visits was 8.49 with a SD of 8.58. The median number of visits was 6. The number of visits ranged from 4-47. After excluding 2 outliers (40 and 47 visits, each $> 3SD$ above the mean) the mean was 6.78 visits with a SD of 3.5 visits.

We estimate a standardized effect size of 0.584 would represent 2-5 emergency visits for alcohol related complaints. This equates to a 29-59% reduction in ED utilization, which is clinically relevant.

Data management plan:

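### The planned per-protocol before-after test selects on attendance after enrolment and is likely to favour even an inert treatment; the plan does not say which analysis governs the conclusion

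*Combined protocol and SAP*

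**What the plan says.** Section IV of the protocol names the predictor variable as "Multi-modal treatment with Extended Release Naltrexone and case management". The outcome for statistical analysis is each patient's alcohol-related ED visits in the 12 months after enrolment minus those in the 12 months before.

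Under potential confounding variables or covariates it says: "There are several potential confounders which we will measure such as number of doses of XR-NTX received". Its answer to confounding is the within-patient change: "The primary strategy employed to combat these cofounders is the selection of the primary outcome". The same section already lists doses received, and the intervals between them, among the feasibility outcomes.

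On analysis sets it says: "We intend to conduct both an intention to treat analysis and a per protocol analysis". The only method given is "Statistical Test: Paired T Test". The per-protocol set is not defined, and neither analysis is named as the one that decides.

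Three other places matter:
- Section II, Handling of missed injection visits: a patient who cannot rebook a missed injection within a month leaves the study. A patient rebooking at 2-4 weeks who reports opiate use cannot resume treatment through it.
- Section II, Follow up procedures after visit 3: an analyst completes the outcome data at 12 months from the health record and the shared ED information exchange (EDIE).
- Section IV, Sample Size: drop-out is expected to be significant, and drop-outs are replaced.

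**The concern.** A per-protocol set built on completed injections is decided by what happens after enrolment, inside the period in which the outcome is counted. Patients who relapse, use opiates or lose contact miss injections, and they plausibly also have more ED visits that year. Removing them lowers the average after-year count. Unless completion is also tied to the baseline rate, the before-year count stays where it was. The difference then appears as a fall that treatment did not cause.

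At stake is how a small single-arm result is read. A significant per-protocol fall beside a flat all-enrolled result could be taken to mean that patients who take the drug benefit, and the plan has no rule against that reading. The study is meant to lead to a randomised trial, so such a figure could also pass into that trial's design.

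The confounder label is a smaller matter. Doses received are part of the treatment. No study doses exist in the before-year, so using patients as their own controls cannot match on them.

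**Working it through.** **1. The plan's own target.** The plan says "We will enroll 25 patients" and "We estimate a standardized effect size of 0.584 would represent 2-5 emergency visits for alcohol related complaints". It states neither alpha nor power. Assuming two-sided 0.05 and 80%, the exact noncentral-t calculation for a paired test with n = 25 gives a detectable effect of 0.584 (power 0.800), so the figure reproduces. On the visit scale:
- 0.584 × 3.5 = 2.04 visits, and 2/6.78 = 29.5% (two outliers removed)
- 0.584 × 8.58 = 5.01 visits, and 5/8.49 = 58.9% (all patients)

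The 2-visit end therefore belongs to mean 6.78, SD 3.5, and the 5-visit end to mean 8.49, SD 8.58.

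**2. What selection must do.** Let a fraction p complete, and let the mean change over everyone be 0. Then p × (completers' change) + (1 − p) × (non-completers' change) = 0. A completer fall of F therefore needs a gap between the groups of F/(1 − p). For F = 2.04 the gap is 2.9 visits at p = 0.3, 4.1 at p = 0.5 and 10.2 at p = 0.8. High completion protects; low completion does not.

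**3. Simulation with an inert treatment.** Per-protocol is taken to mean completing the injections. The documents give no completion rate, no link between attendance and outcome, and no year-to-year variation, so these are assumptions:
- before-year count: Poisson(λ), with λ gamma. One version has mean 8.49 and shape 4; the other has mean 6.78 and SD 3.5, so shape = 6.78²/(3.5² − 6.78) = 8.4
- after-year count: Poisson(λ × exp(u − s²/2)), u normal with SD s = 0.4, 0.6 or 0.8
- completion: logistic in u, with odds of not completing 1.5, 2 or 3 times higher per SD of u; 40%, 50% or 60% complete
- completion does not depend on λ

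This gives 27 settings per baseline, with 400,000 patients each.

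| Baseline mean | All-enrolled change | Per-protocol change | Settings with a fall of 2 or more |
|---|---|---|---|
| 8.49 | about 0 | −0.5 to −3.3 visits (−6% to −39%) | 7 of 27 |
| 6.78 | about 0 | −0.4 to −2.6 visits (−6% to −38%) | 3 of 27 |

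No setting reaches 5 visits. In the mean-8.49 version the completers' before-year mean stays at about 8.5, so the fall comes entirely from the after-year.

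**4. False-positive rate.** With 25 enrolled, the per-protocol test has about 0.4 × 25 = 10 to 0.6 × 25 = 15 patients. It shows a significant reduction in about 6-45% of trials, against 2.5% nominal in that direction. The all-enrolled test does so in about 3-9%. Its excess over 2.5% comes from skewed counts, not selection, so 3-9% is the fair comparator.

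**5. Cross-check with a normal model.** Per-protocol fall = ρ × SD × φ(z_p)/p, where ρ is the correlation between attendance and a better change. With SD 3.5 and ρ = 0.5:
- p = 0.3: 2.03 visits
- p = 0.5: 0.5 × 3.5 × 0.798 = 1.40 visits
- p = 0.8: 0.61 visits

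Reaching 0.584 SD needs ρ = 0.50 at 30% completion, 0.584/0.798 = 0.73 at 50%, and 0.91 at 60%; at 70% or more it cannot be reached. The same correlations apply to 5.01 visits with SD 8.58, because both ends equal 0.584 SD.

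**6. Left out.** Entry on a visit threshold brings regression to the mean. A gamma-Poisson fit to the outlier-excluded figures, truncated at 4 or more visits, puts it at about 1.15 visits. It affects the all-enrolled result too, so it is a separate matter.

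**The case against.** Several objections have force.

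**Doses are only to be measured.** A reader might infer that listing doses as a confounder already conditions the analysis on attendance. The documents do not support that. The stated remedy is the change score, and the only test is an unadjusted paired t test. For doses the defect is the label, although a heading that mentions covariates leaves the door open to adjustment.

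**The target is mostly not reached.** A reader might infer that an inert treatment would show a per-protocol fall as large as the planned target. That holds only at the 2-visit end and only under stronger selection. On mean 8.49, 4 of 27 settings reach 29%, all with odds 3 and s of 0.6 or more. The matching target for that baseline is 5 visits or 59%, which none reaches. In SD units the largest fall is 0.53, below 0.584. The plan's claim, "This equates to a 29-59% reduction in ED utilization, which is clinically relevant", is therefore not matched by selection alone in general.

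**The direction is built in.** The simulation ties completion to the after-year only. If heavier baseline users also drop out, both counts fall and the bias shrinks. The documents do not settle this.

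**The plan is already cautious.** Intention to treat is planned, bias is called substantial, the limits of the sample size are admitted, and ED visits are presented as pilot data. This stands as mitigation. But the bias is attributed to lack of randomisation and blinding and to loss to follow-up, not to choosing patients by attendance, and no analysis is given precedence.

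**Conclusion.** The point stands for the per-protocol test. It selects on events in the after-year and is likely to show a fall under an inert treatment: about 0.4 to 3.3 visits, with a false reduction in about 6-45% of trials against about 3-9% for all enrolled. These sizes rest on the assumed completion rates, selection strength and year-to-year variation, on completion being unrelated to baseline rate, and on per-protocol meaning injections completed. The direction is more secure than the size. Reaching the 2-visit end of the target takes stronger selection, and no simulated setting reaches 5.

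The case for change does not depend on reaching the target; a false-positive rate several times nominal in most settings is enough. Calling doses received a confounder is a mislabel that does no harm unless doses are later adjusted for.

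**What to change.** - State that any conclusion on ED visits rests on all enrolled patients, using health-record and EDIE counts for the full 12 months. Include patients who drop out and are replaced. Section II (Overview of Design) ends enrolment once 25 are retained, while Section IV (Sample Size) replaces drop-outs until 25 are recruited. If replaced patients were left out, the intention-to-treat result would carry the same selection.
- Define the per-protocol set in advance. Report it descriptively beside non-completers, before and after, with no test and no effect claim.
- Move doses received from the confounder list to the feasibility and exposure measures, where the plan already has them.

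Starting the count only after the injection period would not be a substitute. It changes the time window but not who attends, and it needs visit timing although the data management plan exports no dates.

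The cost is wording, and the per-protocol result loses its p-value. The sponsor should confirm that record review continues for patients who leave treatment early, since the whole approach relies on it.

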This is a phase 4 open label feasibility study of extended release naltrexone (Vivitrol, Alkermes Pharmaceutical), case management and tele-addiction medicine for treatment of alcohol use disorders in the ED. The planned study period is 2 years. During this time we will conduct necessary department staff training and recruit 25 patients. Each patient will be followed for 12 months from index visit by our study staff, with case management provided by a full-time research case manager. Patients will be enrolled consecutively, 24 hours a day, 7 days a week. Recruitment will take place in the UCSF Emergency Department, Parnassus campus. Follow up visits may occur in the UCSF ED or an outpatient setting agreed upon by the patient and the research case manager. Patients who drop out of the study will be replaced with new patients; enrollment will end once 25 patients have been retained in the study or at the planned end date.

Initial Screening:

All adult patients presenting to the University of California San Francisco ED during the study period will be screened for frequent ED utilization (defined as 3 or more ED visits in the past 12 months including the index visit) by electronic medical record review conducted by the treating physician or member of the research team. UCSF, San Francisco General, and several other academic and community emergency departments in the San Francisco Bay Area share an electronic platform called the Emergency Department Information Exchange, or EDIE, that documents dates of ED visits and diagnoses. UC emergency providers can view visits at each of these sites, and ED visits to any hospital will be counted towards this 3-or-more threshold.

Determination of Eligibility:

An ED provider or staff (including physicians, advanced health practitioners, nurses, social workers, and case managers) may alert the PI or research study staff of potentially eligible patients based on the initial screen. The research team member will then determine eligibility as described below.

The PI [name], research fellow [name] or study staff (the research case manager) can all determine study eligibility. Initial eligibility will be determined based on chart review during the time of an ED visit. During study hours, the above mentioned faculty and staff will examine the

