ED trackboard to determine if any patients currently in the ED at UCSF have made at least 4 ED visits in the past 12 months to UCSF or a combination of UCSF, ZSFG, or other hospitals based on shared data in our emergency department information exchange platform. If an individual is determined to be eligible based on these criteria, the faculty or study staff will review the chart for the most recent lab results including liver function tests (AST, ALT), platelets, and urine or serum pregnancy tests and urine toxicology testing specifically the presence of opioids including fentanyl (see exclusion criteria for specific cut off values). They will also review the past medical history and allergies in the electronic medical record to determine if the patient has cirrhosis or a document allergy to naltrexone or inactive ingredients contained in naltrexone XR. When a patient is determined to meet criteria inclusion by electronic record review, a study staff member will discuss the case with the ED provider caring for the patient to confirm the patient is willing to be approached, is clinically sober, and medically stable. The ED provider will then introduce the patient to the research staff who will discuss the study with the patient. The research staff member will assess the patient's willingness to participate. If a patient expresses interest in participating the research staff member will confirm the accuracy of information obtained from the medical record review that pertains to inclusion and exclusion criteria. If no discrepancies are found the research team member describe the study in detail and will perform a capacity assessment using the University of California San Diego Brief Assessment of Capacity to Consent to Research (UBACC) if there are any concerns about the participant's capacity to consent, such as ongoing alcohol or drug intoxication or withdrawal.

Capacity Assessment:

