Patients who miss scheduled follow up injection visits will be contacted and asked to reschedule their injection visit as soon as possible. If they are able to reschedule within 2 weeks then no changes to study procedure are necessary. If they are able to reschedule within 2-4 weeks then they will be asked if they have used any opiates (including fentanyl) in the past 7 days. If they have not used opiates in the past 7 days then they will resume treatment, provided they are not endorsing any signs or symptoms of liver injury. If they endorse signs or symptoms of liver injury they will undergo screening as outlined above. If they endorse using opiates then they will not be allowed to resume treatment through the study. If a patient is unable to reschedule a missed injection appointment within one month they will not be allowed to continue in the study. If a patient is unable to resume treatment through the study then they will be provided with alternative follow up options (see transition to ongoing care).

Participant Payment:

A 20-dollar gift card incentive will be used to encourage attendance at the 6 monthly follow up visits required for XR-Naltrexone injections. Gift cards will be given at each of the six visits. The total value of gift cards available to each participant during the study period is \$120.00. Gift cards will be issued for locations that do not sell alcohol (e.g. Starbucks coffee).

Study Subjects:

The target population is patients with frequent ED visits for alcohol related complaints who may benefit from ED-initiated XR-NTX. The accessible population is all people in the San Francisco Bay Area presenting to the ED with an alcohol related complaint. The study sample will be adult

patients presenting to the UCSF ED with active hazardous or high risk alcohol use and ≥ 4 ED visits in the past 12 months for alcohol related complaints.

Inclusion Criteria:

- Age ≥ 21
- AUDIT score ≥ 8
- Frequent emergency department visits, defined as: At least 3 emergency department visits for in the past 12 months, including the index visit.

Exclusion Criteria:

- Opioid use: currently receiving opioid analgesics, self-report of opioid use in past 7 days, current physiologic opioid dependence, patients in acute opioid withdrawal, urine toxicology screen positive for opiates including fentanyl
- History of hypersensitivity to naltrexone, polylactide-co-glycolide (PLG), carboxymethylcellulose, or any other components of the diluent

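### The 12-month ED-visit count that admits patients is also the baseline of the pilot primary outcome, so part of any before/after fall is expected with no treatment effect

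*Combined protocol and SAP*

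**What the plan says.** All places are in the combined protocol and SAP.

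- **Entry rule.** Section II, Initial Screening, sets frequent use as "defined as 3 or more ED visits in the past 12 months including the index visit". The Inclusion Criteria agree: "At least 3 emergency department visits for in the past 12 months, including the index visit". Determination of Eligibility instead looks for patients who "have made at least 4 ED visits in the past 12 months". Study Subjects describes "patients presenting to the UCSF ED with active hazardous or high risk alcohol use and ≥ 4 ED visits in the past 12 months", and that sentence goes on to restrict the visits to alcohol-related ones. The threshold (3 or 4) and the type of visit (any cause or alcohol-related) must be reconciled.
- **Outcome.** Section IV defines the pilot primary outcome as visits in the 12 months after enrolment minus the number "of ED visits for alcohol related complaint in 12 months before enrollment".
- **Protection against confounding.** Section IV names the choice of this outcome as its main strategy, because "Since the outcome is a change from the patient's baseline ED usage from the prior year each patient serves as their own control".
- **Inference.** Statistical issues specifies a paired t test and a causal hypothesis, worded as follows: "ED initiated Treatment of alcohol use disorders with multi-modal therapy reduces alcohol related ED visits in patients with frequent ED visits for alcohol related complaints". The Cost analysis paragraph adds cost per avoided ED visit and programme cost against medical cost saved.
- **Caveats given.** Section IV calls the risk of bias substantial because everyone is treated, there is no randomisation or blinding, and loss to follow-up is likely. It disclaims precise estimates of efficacy or cost. It does not mention regression to the mean, a comparison group, or a baseline window separate from the selection window.

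**The concern.** A patient's yearly count is a personal rate plus chance, and the rate itself may change. Admitting only patients whose count reached a threshold over-represents those whose year ran high. Their expected count next year is lower even if treatment does nothing. Comparing each patient with himself or herself does not help, because the comparison year is the one that was selected. Counting the index visit adds to the gap: every enrolled patient has it in the before year by construction, and nothing in the after year corresponds to it.

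Two outputs are at stake. A significant paired t test could be read as evidence for the causal hypothesis. Visits that would have gone away anyway could be booked as avoided, and the cost analysis is meant to guide later research, with a randomised trial planned next.

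**Working it through.** **1. The plan's own figure.** The inputs are n = 25 and a paired t test. Alpha, sidedness and power are not stated. At two-sided 5% and 80% power, the noncentral t gives a detectable standardised effect of 0.584, as stated. In visits, 0.584 × 3.5 = 2.04 and 2/6.78 = 29%; 0.584 × 8.58 = 5.01 and 5.01/8.49 = 59%. The range of 2 to 5 visits (29–59%) reproduces.

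**2. No-treatment change, selecting on a fixed 12-month count.** The reference data in the Sample Size paragraph ("Last year 42 patients presented to the UCSF Emergency Department at least 4 times for an alcohol related complaint") have mean 8.49, SD 8.58 and median 6, or mean 6.78 and SD 3.5 without two outliers. Two models were tuned to them.

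*Gamma-Poisson, fitted to 6.78 and 3.5 among those with 4 or more visits.* Shape k = 0.2564 and population mean m = 1.0290. With a stable personal rate, the expected next-year count is (x + k) × m/(m + k), where m/(m + k) = 1.0290/1.2854 = 0.8005.

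- 4 or more: (6.78 + 0.2564) × 0.8005 = 5.63, a fall of 1.15 (17%).
- 3 or more: (5.62 + 0.2564) × 0.8005 = 4.71, a fall of about 0.9 (16%).

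*Lognormal-Poisson, log-rate mean −0.35 and SD 1.35.* Among those with 4 or more visits this gives mean about 8.4, SD 8.5–8.9 and median 6. The next-year mean with stable rates is 7.28, a fall of 1.1 (13%).

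The documents give no year-to-year correlation of personal rates, so the last column rests on an assumption.

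| Rule | Model | Stable rates | Correlation 0.8 (assumed) |
|---|---|---|---|
| ≥3 | gamma | 0.9 (16%) | 1.9 (34%) |
| ≥3 | lognormal | 0.9 | 1.8 (27%) |
| ≥4 | gamma | 1.15 (17%) | 2.4 (36%) |
| ≥4 | lognormal | 1.1 (13%) | 2.4 (29%) |

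**3. Enrolling at an ED visit, which is closer to the trial.** Each simulated patient enters at the first qualifying visit in a 16-month window (Section VI: March 2020 to June 2021). The model is gamma-Poisson with stable rates. Capture is the assumed chance that a qualifying visit leads to enrolment. The last column subtracts 1 from the before count.

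| Rule | Capture | Before | After | Fall, index counted | Fall, index left out |
|---|---|---|---|---|---|
| ≥3 | all | 4.78 | 3.88 | 0.90 | −0.10 |
| ≥3 | 30% | 5.63 | 4.63 | 1.00 | 0.00 |
| ≥4 | all | 5.75 | 4.58 | 1.17 | 0.17 |
| ≥4 | 30% | 6.56 | 5.35 | 1.21 | 0.21 |

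The lognormal model with a 15-month window agrees. Without the index visit the means go from 4.51 to 4.56 (≥3) and from 5.82 to 5.66 (≥4). Over all first-qualifying-visit runs, the fall with the index visit counted was about 0.5 to 1.2 visits.

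Other entry assumptions leave more. Entry at a randomly chosen qualifying visit with stable rates gives 1.3 to 1.5 visits with the index visit and 0.3 to 0.5 without. Weighting patients by their chance of attending over an assumed 15 months, index visit left out, gives 0.6 to 0.9 with stable rates and 1.2 to 1.8 at correlation 0.8.

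**4. Effect on the test.** With n = 25, two-sided 5%, no treatment effect and stable rates, the paired t test declares a reduction in about 34–42% of trials under fixed-count selection and 41–52% under first-qualifying-visit entry with the index visit counted. The nominal rate in that direction is 2.5%. Under random-visit entry, leaving out the index visit brings it to 7–11%.

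**The case against.** The strongest reply is that this is a feasibility study. Feasibility measures are its listed primary outcomes of interest, n = 25 reflects one case manager's load, precise efficacy estimates are disclaimed, and a randomised trial is to follow. The plan also concedes substantial bias because everyone is treated, and it claims matching for many confounders, not all. This stands as far as severity goes: recruitment, retention and dosing results are untouched, and own-control matching is correct for fixed traits. It does not remove the point. Imprecision differs from a bias of known direction, and the plan still states a causal hypothesis, a test and avoided-visit costs.

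The second reply is that the size is assumed, and this stands too. A reader might infer that selection alone could produce most of the 2-to-5-visit range. That requires correlations that the documents do not give. A reader might also infer that the fall persists much the same once the index visit is removed. Under first-qualifying-visit entry with stable rates it nearly disappears. The mismatch between any-cause entry and an alcohol-related outcome could weaken the effect further; it was not modelled.

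Third, the 42-patient cohort looks like a ready control group, but the documents do not support that use. It counts UCSF alcohol-related visits at a threshold of 4, with no AUDIT score, consent or medical exclusions, while enrolled patients can qualify through visits to other hospitals. It is also imprecise. With an SD of change of about 8.9 (lognormal, correlation 0.8), the 95% margin for 25 against 42 patients is 1.96 × 8.9 × √(1/25 + 1/42) = 4.4 visits.

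**Conclusion.** The concern holds in direction and is uncertain in size. The selection year is also the baseline year, so some fall is expected without treatment, and the own-control argument does not address it. The expected no-treatment fall is about 0.9–1.2 visits (13–17%) under fixed-count selection with stable rates, and about 1.8–2.4 (27–36%) at an assumed correlation of 0.8. With entry at the first qualifying visit it is about 0.5–1.2 with the index visit counted, and little or none without it. Against the lower end of the plan's target, 0.5–1.2 is 25–60% of 2 visits. These figures rest on the two count models, on the assumed entry process, and on where the index visit is counted, which the outcome definition leaves open.

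The paired t test alone therefore cannot support the hypothesis, and cost per avoided visit from the raw change would be biased in the treatment's favour. It does not follow that an observed fall would be wholly an artefact, or that the feasibility results are compromised. Severity: should fix.

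**What to change.** 1. Exclude the index visit from the before count, and say so in the outcome definition. Reconcile the entry threshold and visit type across Section II.
2. Limit the own-control sentence in Section IV to stable patient characteristics, and state that the before/after change includes regression to the mean.
3. Report the change descriptively with a confidence interval. State that neither the hypothesis nor avoided-visit or cost-saved figures will be concluded from the raw difference alone. Show cost per avoided visit only as a sensitivity range that includes a no-treatment fall. For illustration, if the observed fall were 2.0 visits and 1.2 were expected anyway, avoided visits drop to 0.8 and the cost per avoided visit rises by a factor of 2.0/0.8 = 2.5.
4. As a descriptive benchmark, have the planned independent analyst run the same EHR/EDIE query for untreated patients who meet the same visit-count rule, and report their next-year change beside that of the enrolled patients. Use the 42-patient cohort only if its rule and hospitals are aligned, and leave out anyone later enrolled.

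Items 1 to 3 cost protocol wording and possibly an IRB note. Item 4 costs a retrospective query, and more work if a new cohort must be assembled. No extra patients or visits are needed. The downside is that the benchmark is historical, imprecise and not matched on AUDIT score or medical exclusions, and the apparent effect will be smaller.
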